Baseline disease characteristics were similar across the treatment groups. Overall, the median (Q1, Q3) baseline HIV-1 RNA value was 4.37 (3.86, 4.74) \log_{10} copies/mL, and the median (Q1, Q3) baseline CD4 cell count was 437 (332, 599) cells/ μ L. Among the 182 participants, most had HIV-1 RNA \leq 100,000 copies/mL (85.2%, 155 participants) and a CD4 cell count range of \geq 350 to $<$ 500 cells/ μ L (31.9%, 58 participants) or \geq 500 cells/ μ L (37.4%, 68 participants).

Efficacy Results:

Primary Efficacy End Point

HIV-1 RNA $<$ 50 copies/mL at Week 54 Using the US FDA-Defined Snapshot Algorithm

The primary analysis at Week 54 demonstrated similar results in each treatment group, with no significant difference between each of the GS-6207-containing groups and the BVY group, as follows:

- GS-6207 total: 136 of 157 participants (86.6%)
- SC GS-6207 + (DVY \rightarrow TAF): 47 of 52 participants (90.4%)
- SC GS-6207 + (DVY \rightarrow BIC): 45 of 53 participants (84.9%)
- Oral GS-6207 + DVY: 44 of 52 participants (84.6%)
- BVY: 23 of 25 participants (92.0%)

For participants with HIV-1 RNA $<$ 50 copies/mL at Week 28, the proportion with HIV-1 RNA $<$ 50 copies/mL at Week 54 using the US FDA-defined snapshot algorithm were also similar in each treatment group, with no significant difference between each of the GS-6207-containing groups and the BVY group, as follows:

- GS-6207 total: 135 of 147 participants (91.8%)
- SC GS-6207 + (DVY \rightarrow TAF): 46 of 49 participants (93.9%)
- SC GS-6207 + (DVY \rightarrow BIC): 45 of 49 participants (91.8%)
- Oral GS-6207 + DVY: 44 of 49 participants (89.8%)
- BVY: 23 of 25 participants (92.0%)

Secondary Efficacy End Points

Week 28

Results from the secondary efficacy analysis of Week 28 data of Study GS-US-200-4334 demonstrated similar results in each treatment group, with no significant difference between each of the GS-6207-containing treatment groups and the BVY treatment group with respect to the proportion of participants with HIV-1 RNA < 50 copies/mL using the US FDA-defined snapshot algorithm, the change from baseline in log₁₀ HIV-1 RNA, and the change from baseline in CD4 cell count.

HIV-1 RNA < 50 copies/mL using the US FDA-defined snapshot algorithm

- GS-6207 total: 147 of 157 participants (93.6%)
- SC GS-6207 + (DVY → TAF): 49 of 52 participants (94.2%)
- SC GS-6207 + (DVY → BIC): 49 of 53 participants (92.5%)
- Oral GS-6207 + DVY: 49 of 52 participants (94.2%)

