8.10. Sample Size

A sample size of 50 participants in Treatment Groups 1 to 3, respectively, was chosen to estimate the response rate of HIV-1 RNA < 50 copies/mL at Week 54. A total sample size of 75 participants for each pair of comparisons (ie, between each of the GS-6207-containing regimen groups [Treatment Groups 1 to 3, n = 50] and the B/F/TAF [Treatment group 4, n = 25]) will provide 39% power to evaluate non-inferiority with respect to the response rate of HIV-1 RNA < 50 copies/mL at Week 54. In this sample size and power calculation, it is assumed a response rate is 90.9% (based on pooled data from studies GS-US-380-1489 and GS-US-380-1490) for each treatment group and a non-inferiority margin is 0.12.

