3. GENERAL CONSIDERATIONS FOR DATA ANALYSES

Analysis results will be presented using descriptive statistics. For categorical variables, the number and percentage of subjects in each category will be presented; for continuous variables, the number of subjects (n), mean, standard deviation (SD) or standard error (SE), median, first quartile (Q1), third quartile (Q3), minimum, and maximum will be presented.

All statistical tests will be 2-sided and performed at the 5% significance level for descriptive purpose unless otherwise specified.

By-subject listings will be presented for all subjects in the All Randomized Analysis Set and sorted by subject identification (ID) number, visit date, and time (if applicable). Data collected on log forms, such as AEs, will be presented in chronological order within the subject. The treatment group to which subjects were randomized will be used in the listings. Age, sex at birth, race, and ethnicity will be included in the listings, as space permits.

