6.1.2. Primary Analysis of the Primary Efficacy Endpoint

The proportion of subjects with HIV-1 RNA < 50 copies/mL as determined by the US FDA-defined snapshot algorithm at Week 54 will be based on the FAS. Point estimates ($P_1 - P_2$) and its 95% confidence interval (CI) for the difference in the response rates between each of the LEN-containing regimen groups (Treatment Groups 1 to 3) and the B/F/TAF group (Treatment Group 4) will be constructed using stratum-adjusted Mantel-Haenszel (MH) proportion as described as follows {Koch 1989}, stratified by baseline HIV-1 RNA level ($\leq 100,000$ copies/mL or $> 100,000$ copies/mL):

$$P_1 - P_2 \pm Z_{(1-\alpha/2)} * SE(P_1 - P_2),$$

where

- $(P_1 - P_2) = \frac{\sum w_h d_h}{\sum w_h}$, is the stratum-adjusted MH proportion difference,

where $d_h = p_{1h} - p_{2h}$ is the difference in the response rate between of the LEN-containing regimen groups (Treatment Groups 1 to 3) and the B/F/TAF group (Treatment Group 4) in stratum h ($h=1$ to 4).

- $w_h = \frac{n_{1h} n_{2h}}{n_{1h} + n_{2h}}$, is the weight based on the harmonic mean of sample size per treatment group for each stratum where n_{1h} and n_{2h} are the sample sizes of the LEN-containing regimen groups (Treatment Groups 1 to 3) and the B/F/TAF group (Treatment Group 4) in stratum h .

- $SE(P_1 - P_2) = \sqrt{\frac{\sum w_h^2 \left[\frac{p_{1h}^* (1 - p_{1h}^*)}{n_{1h} - 1} + \frac{p_{2h}^* (1 - p_{2h}^*)}{n_{2h} - 1} \right]}{(\sum w_h)^2}}$, where $p_{1h}^* = \frac{m_{1h} + 0.5}{n_{1h} + 1}$ and

$p_{2h}^* = \frac{m_{2h} + 0.5}{n_{2h} + 1}$. m_{1h} and m_{2h} are the number of subjects with HIV-1 RNA < 50 copies/mL in the LEN-containing regimen groups (Treatment Groups 1 to 3) and the B/F/TAF group (Treatment Group 4) in stratum h .

- $\alpha = 0.05$ for this study
- $Z_{(1-\alpha/2)} = Z_{0.9750} = 1.96$ is the 97.50th percentile of the normal distribution

Note that if the computed lower confidence bound is less than -1 , the lower bound is defined as -1 . If the computed upper confidence bound is greater than 1 , the upper bound is defined as 1 .

The number and percentage of subjects with HIV-1 RNA < 50 copies/mL at Week 54 will be summarized. The associated p-values will be estimated based on the CMH test stratified by baseline HIV-1 RNA level ($\leq 100,000$ copies/mL or $> 100,000$ copies/mL).

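### Protocol 1.2.2.8 reads a non-significant Week 54 comparison as similarity, but the reported counts (unstratified) do not exclude a 12-point deficit against B/F/TAF for any lenacapavir group

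*Protocol*

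**What the plan says.** **The result.** Protocol 1.2.2.8, under the primary efficacy end point, presents the Week 54 snapshot outcome as demonstrating that the groups are alike, "with no significant difference between each of the GS-6207-containing groups and the BVY group". It lists responders by group and gives no difference, interval or p-value. Similar wording is used there for Week 28 and for Weeks 38 and 54 together.

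**The plan.** Protocol 8.5.1 and SAP 6.1.2 call for the difference between each lenacapavir group and B/F/TAF with a 95% CI. In the SAP this "will be constructed using stratum-adjusted Mantel-Haenszel (MH) proportion as described as follows". A p-value comes second: "The associated p-values will be estimated based on the CMH test stratified by baseline HIV-1 RNA level". Protocol 8.5.1 calls these p-values nominal. Neither section says how the interval or the p-value is to be read.

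**The margin.** It appears only in the sample-size text (Protocol 8.10, SAP 1.3). There, 50 against 25 participants "will provide 39% power to evaluate non-inferiority with respect to the response rate of HIV-1 RNA < 50 copies/mL at Week 54", assuming 90.9% response "for each treatment group and a non-inferiority margin is 0.12".

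**The status of the trial.** Protocol 8.2.1.2 and SAP 2.1.1 say the study lacks adequate power for a formal efficacy evaluation. SAP 3.5 calls it non-confirmatory, and SAP 3 adds: "All statistical tests will be 2-sided and performed at the 5% significance level for descriptive purpose unless otherwise specified".

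**The concern.** A test that fails to reject equality supports similarity only if it would probably have rejected when a difference that matters was present. Here the control group has 25 participants, and two of the three observed differences are deficits of about 7 points. A reader of 1.2.2.8 is told that similarity was demonstrated and is given no interval from which to see how large a deficit remains possible. The only size of deficit that the documents put a number on is 12 points. What is at stake is what the primary result can be said to show, in a study whose data are meant to support further development (Protocol 1.7).

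**Working it through.** **1. The stated power.** Inputs from Protocol 8.10: 90.9% in both groups, margin 0.12, 50 against 25. That paragraph gives no alpha, so I take two-sided 5% from SAP 3.

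- SE = √[0.909 × 0.091 × (1/50 + 1/25)] = 0.0704
- Power = Φ(0.12/0.0704 - 1.96) = Φ(-0.257) = 39.9%

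The stated 39% is reproduced to within a point. It is power for non-inferiority. One-sided 5% would give 52.3%, which does not fit.

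**2. Power of the equality test.** Same group sizes, control 90.9%, two-sided 5%, power = Φ[(d - 1.96 × SE₀)/SE₁], with SE₀ pooled and SE₁ unpooled.

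- d = 0.12: SE₀ = 0.0922, SE₁ = 0.0815, power = Φ(-0.746) = 23%
- d = 0.071: SE₀ = 0.0846, SE₁ = 0.0776, power = Φ(-1.221) = 11%

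With a true deficit of 12 points, the test would come out non-significant about three times in four.

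**3. Week 54 differences from the reported counts.** Control 23/25 = 92.0%. The Wald interval is d ± 1.96 × √[p₁(1-p₁)/n₁ + p₂(1-p₂)/n₂]. For Group 1, 47/52 = 90.4%, SE = 0.0679, and -1.6 ± 13.3 gives -14.9 to 11.7.

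The SAP 6.1.2 standard error uses p* = (m+0.5)/(n+1) and n-1. Taken over a single stratum, Group 1 has p₁* = 47.5/53 = 0.896, p₂* = 23.5/26 = 0.904 and SE = 0.0738, so the lower bound is -16.1.

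| Group | Responders | Difference (points) | Wald 95% CI | Lower bound, SAP SE (one stratum) | Lower bound, Newcombe / Miettinen-Nurminen |
|---|---|---|---|---|---|
| 1 | 47/52 | -1.6 | -14.9 to 11.7 | -16.1 | -14.0 / -14.5 |
| 2 | 45/53 | -7.1 | -21.4 to 7.3 | -22.5 | -20.4 / -21.1 |
| 3 | 44/52 | -7.4 | -21.9 to 7.1 | -22.9 | -20.8 / -21.5 |

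Every lower bound is below -12 and every upper bound is above 0. So it is correct that no difference was significant (Fisher p = 1.00, 0.49 and 0.49), but that does not show similarity.

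**4. The planned, stratified interval.** Responders by group and stratum are not given, so the stratum layout has to be assumed. Overall, 155 of 182 participants were at or below 100,000 copies/mL, which leaves 27 (14.8%) above. In proportion, that is 52 × 0.148 = 7.7 per lenacapavir group and 25 × 0.148 = 3.7 in the control group. I applied the SAP formula to every split of the failures between the strata.

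- *Near-proportional strata (7 or 8 high in the lenacapavir group, 3 or 4 in control).* The lower bound runs from -17.7 to -11.0 for Group 1, from -24.1 to -15.1 for Group 2 and from -24.6 to -15.1 for Group 3. Group 1 rises above -12 in 2 of 72 layouts; both need 3 high-stratum controls and every failure in both groups to fall in the high stratum.
- *Wider range (4 to 13 high against 2 to 7).* The bound is below -12 in 989 of 1,062 layouts for Group 1 (93%), 1,421 of 1,440 for Group 2 (99%) and 1,422 of 1,440 for Group 3 (99%). These are counts of layouts, not probabilities.

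**5. The subset suppressed at Week 28.** Section 1.2.2.8 repeats the phrase for this subset. There Group 1 (46/49 against 23/25) has a lower bound of -10.7 by Wald, or -11.95 with the SAP standard error over one stratum. The Week 54 finding therefore does not carry over to it.

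**The case against.** The strongest reply is that nothing in the plan was violated. The margin serves only the sample-size text, and no objective, endpoint or hypothesis uses it. The sample size was chosen to estimate response rates, tests are descriptive, and the trial is non-confirmatory. The planned analysis already leads with the difference and its CI. The text in question is a background summary of two clinical study reports that are not available here, and those reports may well give the intervals.

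All of that stands, and it rules out several stronger readings that a reader might infer:

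- *That the trial failed its own non-inferiority criterion.* No such criterion was set and no such claim is made.
- *That the plan offers only an equality test.* It specifies the interval first.
- *That 39% is the power behind the non-significant result.* It is non-inferiority power; the equality test has less.
- *That the trial's conclusions rest on similarity.* The conclusions that close 1.2.2.8 speak of high suppression rates and give 86.6% and 92.0%, without mentioning similarity.
- *That the data show inferiority.* Every Week 54 interval includes zero.

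The reply does not rescue the sentence itself. A study described as inadequately powered for formal efficacy evaluation cannot demonstrate similarity through a non-significant test, and a background summary is still read by investigators and ethics committees.

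**Conclusion.** The concern holds as a fault of interpretation at the Week 54 primary endpoint in the full analysis set. The reported counts are compatible with deficits of up to about 15 points in Group 1 and about 21 to 22 points in Groups 2 and 3 (Wald). A 12-point deficit is not excluded for any group by any of the four unstratified methods.

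This rests on unstratified intervals. The planned stratified interval would very probably give the same answer for Groups 2 and 3. For Group 1 it would do so in nearly all assumed layouts, but not in every one. Twelve points is used only as the one reference size that the documents supply.

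**What to change.** - **Protocol 1.2.2.8, Week 54.** Replace the similarity and no-significant-difference wording with each difference and its planned stratified 95% CI. Say that the study was not powered to exclude a 12-point deficit. Say also that Week 54 does not exclude one, after checking this against the stratified intervals, above all for Group 1.
- **Protocol 1.2.2.8, Weeks 28 and 38.** Make the same replacement. Use the SAP formula at Week 28, where the control group is 25/25 and contributes no variance to a Wald interval.
- **Protocol 8.5.1 and SAP 6.1.2.** Add a sentence that comparisons are interpreted descriptively from the 95% CI, with the 0.12 sample-size margin as a reference, and that the nominal CMH p-value is not evidence of similarity.
- **Do not add a non-inferiority decision rule.** The Week 54 results are already known and the trial is declared non-confirmatory.

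The cost is wording and the retrieval of intervals that are already planned; no new data are needed. The downside for the sponsor is that the result reads less favourably.

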1.3. Information About Bictegravir

Bictegravir (BIC, B) is a potent integrase strand transfer inhibitor (INSTI) that has been evaluated for the treatment of HIV-1 infection and that has demonstrated a terminal half-life suitable for once daily administration without a boosting agent.

1.3.1. General Information

For further information on BIC, please refer to the IB. Information in the IB includes:

- Nonclinical PK and in vitro metabolism
- Nonclinical pharmacology and toxicology
- Clinical experience

1.4. Information About Tenofovir Alafenamide

Tenofovir (TFV) is a nucleotide analog with limited oral bioavailability that as its intracellular active moiety, tenofovir diphosphate (TFV-DP), inhibits HIV-1 reverse transcription. Tenofovir alafenamide (TAF) is an oral phosphonamidate prodrug of TFV. Tenofovir alafenamide is more stable in plasma than tenofovir disoproxil fumarate (TDF), provides higher intracellular levels of the active phosphorylated metabolite TFV-DP to target cells.

1.4.1. General Information

For further information on TAF, please refer to the IB. Information in the IB includes:

- Nonclinical PK and in vitro metabolism
- Nonclinical pharmacology and toxicology
- Clinical experience

1.5. Information About Emtricitabine/Tenofovir Alafenamide

Tenofovir is a nucleotide analog with limited oral bioavailability that as its intracellular active moiety, TFV-DP, inhibits HIV-1 reverse transcription. Tenofovir alafenamide is an oral phosphonamidate prodrug of TFV. Tenofovir alafenamide is more stable in plasma than TDF, provides higher intracellular levels of the active phosphorylated metabolite TFV-DP to target cells. TAF in combination with emtricitabine (FTC) (F/TAF) forms an N(t)RTI backbone that can be combined with different third agents for the treatment of PLWH.

In 2016, US and international guidelines for the treatment of HIV infection were updated to include F/TAF as part of several recommended regimens for initial treatment of ART-naive, PLWH {[Panel on Antiretroviral Guidelines for Adults and Adolescents 2016](#), [Saag 2018](#)}. In both current guidelines ({[Department of Health and Human Services \(DHHS\) 2011](#), [European AIDS Clinical Society \(EACS\) 2018](#)}), F/TAF is recommended for initial therapy in most PLWH in combination with an INSTI, specifically dolutegravir or BIC (available as BIKTARVY® [BVY, B/F/TAF]), or raltegravir (RAL).

1.5.1. General Information

For further information on F/TAF, please refer to the IB. Information in the IB includes:

- Nonclinical PK and in vitro metabolism
- Nonclinical pharmacology and toxicology
- Clinical experience

1.6. Information About Bictegravir/Emtricitabine/Tenofovir Alafenamide

Bictegravir/F/TAF is a fixed-dose combination (FDC) tablet for the treatment for HIV-1 infection. The B/F/TAF FDC tablet is a safe and highly effective INSTI-based treatment regimen, offering minimal pill burden, once-daily dosing, and excellent tolerability. The B/F/TAF FDC is a recommended initial treatment for PLWH {[Department of Health and Human Services \(DHHS\) 2013](#)}.

1.6.1. General Information

For further information on B/F/TAF, please refer to the IB. Information in the IB includes:

- Nonclinical PK and in vitro metabolism
- Nonclinical pharmacology and toxicology
- Clinical experience

1.7. Rationale for This Study

Advances in ART have led to significant improvements in morbidity and mortality among people living with HIV by suppressing viral replication, preserving immunologic function, and averting disease progression to AIDS. While combination ARV therapy for the treatment of HIV-1 infection has been largely successful in reducing the morbidity and mortality associated with HIV disease, there remains a significant medical need for new well-tolerated therapies that take into consideration HIV genetic variability, ARV resistance, and new options for regimen simplification.

The goal of this study is to systematically evaluate potential combination regimens containing the novel capsid inhibitor, GS-6207, in treatment-naïve PLWH as an induction regimen and in virologically-suppressed people as a maintenance regimen. Participants who do not meet criteria for viral suppression will not be permitted to initiate a maintenance regimen using fewer agents than the induction regimen. The data are intended to support the ongoing clinical development of SC and oral GS-6207 for PLWH. The regimen of oral GS-6207+F/TAF will provide a positive control for the dual agent maintenance groups as well as support this combination for further development. An active control group of B/F/TAF is included as a current standard-of-care comparator.

1.8. Rationale for Dose Selection

1.8.1. GS-6207

The dose selection for GS-6207 in this study is supported by antiviral activity, PK, and safety data from the ongoing Phase 1b POC (study GS-US-200-4072) in treatment-naïve and treatment experienced but CAI-naïve PLWH, as well as PK and safety data from the two Phase 1 studies in healthy volunteers (Studies GS-US-200-4538 and GS-US-200-4071).

In the ongoing Phase 1b POC study (GS-US-200-4072), potent antiviral activity of GS-6207 has been demonstrated; the mean maximum HIV-1 RNA decline over 10-day monotherapy after single SC doses of 50 mg to 450 mg was 1.8 to 2.2 log₁₀ copies/mL, respectively. All participants achieved at least 1 log₁₀ copies/mL decline in their HIV-1 RNA at Day 10. Day 10 antiviral activity was comparable across a single dose range of 50 mg to 450 mg. At these doses, mean (% CV) GS-6207 concentrations on Day 10 were 1.1- to 9.9-fold higher (ie, IQ 1.1 to 9.9) than the protein adjusted (pa)EC₉₅ for wild type HIV-1 (paEC₉₅ = 3.87 ng/mL in MT-4 cells) (see Section 1.2.2.2).

Based on these data and the safety data available to date, a concentration target of at least 15.5 ng/mL for C_{trough} (corresponding to IQ4 based on paEC₉₅ from MT-4 cells) has been selected to ensure adequate antiviral activity would be achieved throughout dosing. GS-6207 formulations and doses to be evaluated in this study are informed by PK and safety data from Phase 1 studies, GS-US-200-4071 and GS-US-200-4538, in healthy volunteers.

In Treatment Groups 1, 2 and 3, the proposed GS-6207 regimens target an exposure whereby the lower bound of the 90% CI of the C_{trough} is at least 4-fold higher than the paEC₉₅ (ie, IQ4; 15.5 ng/mL) starting within a few days of dosing initiation and maintained throughout the dosing interval.

In Treatment Groups 1 and 2, participants will receive a SC GS-6207 regimen (every 26 weeks), preceded by an oral PK loading regimen. As described in Section 1.2.2.5, GS-6207 SC Injection (309 mg/mL) exhibits a slow initial release necessitating oral PK loading prior to the first SC injection to achieve IQ4 within a few days of initiation of dosing, participants will receive oral tablet doses of GS-6207 600 mg on Days 1 and 2, and 300 mg on Day 8. Participants will then receive GS-6207 927 mg SC on Day 15, followed by GS-6207 927 mg SC administered every 6 months (every 26 weeks). This regimen is projected to achieve target exposures within a few days of initiation, and to maintain throughout the 26 weeks SC dosing interval.

In Treatment Group 3, participants will receive an oral daily regimen of GS-6207. Participants will receive oral tablet doses of GS-6207 600 mg on Days 1 and 2, as a PK load, and 50 mg once daily, starting from Day 3. This regimen is projected to achieve target exposures within a few days of initiation. Based on available PK data (GS-US-200-4071), GS-6207 50 mg once daily is predicted to achieve a similar C_{max} as GS-6207 927 mg SC, administered every 26 weeks in Treatment Groups 1 and 2.

Safety data from studies GS-US-200-4071 and GS-US-200-4538 demonstrated favorable safety and tolerability profile of GS-6207 administered as single oral doses of up to 1800 mg, multiple oral daily doses of up to 100 mg or single SC doses of up to 927 mg. GS-6207 exposures in this study are predicted to be within the range of those shown to be safe and well tolerated; thereby, supporting further evaluation of this regimen in this study.

1.8.2. F/TAF and TAF

In Cohorts 1, 2 and 3, participants will receive F/TAF once daily (during the induction phase for Cohorts 1 and 2, and throughout Cohort 3), and in Cohort 1, participants will receive oral once daily TAF 25 mg during the maintenance period in combination with SC GS-6207. Both the F/TAF FDC containing F (200 mg) and TAF (25 mg), and TAF 25 mg single agent have been approved by the US Food and Drug Administration (FDA) as a component of several regimens, for use once daily for the treatment of HIV-1 infection in adults, or for treatment of hepatitis B virus (HBV) {BIKTARVY 2019, DESCOVY® 2017, VEMLIDY® 2019}.

